Pioglitazone has been studied in randomized clinical studies as a treatment for subjects already exhibiting clinical symptoms of either mild cognitive impairment (MCI) or probable AD, with mixed results. Geldmacher et al conducted an 18-month, double-blind, placebo-controlled randomized trial to test long-term safety and tolerability of pioglitazone in a nondiabetic elderly population with AD [15]. Twenty-nine subjects were treated with pioglitazone titrated to 45 mg/day (n=14; mean age = 74.9) or matching placebo (n=15; mean age = 67.0 years). Subjects maintained treatment with cholinesterase inhibitors and could begin memantine therapy when it became available during the study. The primary outcome of this study was the frequency of adverse events (AEs), while secondary outcomes included measures of cognition, activities of daily living, neuropsychiatric symptoms (NPS), and global functioning. Pioglitazone was generally well tolerated in this pilot study, as no serious AEs (SAEs) or unanticipated AEs

CONFIDENTIAL

occurred, while peripheral edema was the principal AE (28.6% in pioglitazone-treated subjects compared with 0% in placebo-treated subjects). No significant treatment effect was observed on exploratory analysis of clinical efficacy.

Sato et al conducted a 6-month, randomized, open-controlled pilot study of pioglitazone efficacy on cognition, regional cerebral blood flow (rCBF), and plasma A β 40 and A β 42 [16]. Study subjects were 42 AD patients with T2DM, half of whom were treated with 15 to 30 mg pioglitazone daily; all subjects continued on their previous T2DM treatment (including sulfonylureas, biguanides, and α -glucosidase inhibitors). Subjects receiving pioglitazone demonstrated significantly improved cognition (Mini-Mental State Examination [MMSE], Alzheimer's Disease Assessment Scale-Cognitive Subscale [ADAS-cog]), Wechsler Memory Scale-revised logical memory-I) and rCBF at 6 months compared to baseline (Visit 2), while untreated subjects did not. Untreated subjects did, however, have increased plasma A β 40 /A β 42 ratio, while there was no significant change in pioglitazone-treated subjects.

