Few postmarketing reports of new-onset or worsening diabetic macular edema with decreased visual acuity have occurred with TZDs, including pioglitazone. Many of these patients reported concurrent peripheral edema. It is not known whether there is a direct association between pioglitazone and macular edema, but investigators should be alert to the possibility of macular edema. If study participants report disturbances in visual acuity (eg, blurred vision, distortion of images, missing areas, dimming or “graying-out” of vision from loss of contrast sensitivity, and changes in the way color is perceived), they will be evaluated by an ophthalmologist.

There have been postmarketing reports of bone fractures associated with the use of TZDs, including pioglitazone. The majority of the fractures occurred in women with most of the fractures involving upper and lower limbs of the body. Many cases lack any information about history or about risk factors for bone fractures. In cases where information was available, patients had a history of and multiple risk factors for fractures.

Adverse events associated with pioglitazone, listed in the Warnings and Precautions section of the Company Core Data Sheet [20], for subjects with T2DM and at doses considerably higher (15-45 mg) than the intended dose in this clinical development program (sustained release [SR] 0.8 mg) were as follows: congestive heart failure (CHF) and peripheral edema due to dose-related fluid retention, hepatic failure, increased incidence of fractures in female population, hypoglycemia, macular edema, and bladder cancer. A detailed discussion of the safety profile of pioglitazone is provided in the investigator’s brochure.

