6.3.2 Study Dose

Because studies for AD prevention require long treatment durations and large study populations, it is not practical to do typical phase 2 studies prior to initiating phase 3 studies. As such a phase 2 program (including dose finding) was not conducted prior to the AD-4833/TOMM40_301 study. Still, there are a number of preclinical studies that indicate that pioglitazone increases mitochondrial numbers, motility and function at very low doses (relative to doses used to treat T2DM) [7]. This effect on mitochondria is hypothesized to be the key mechanism of action (MOA) for pioglitazone's ability to delay the onset of MCI due to AD. In addition to these preclinical studies, an imaging study (using functional magnetic resonance imaging [fMRI] was carried out in cognitively normal elderly subjects). From this study, it was ascertained that pioglitazone has central nervous system (CNS) effects at low doses and that there is a demonstrable blood oxygen level-dependent (BOLD) effect in the left hippocampus during an encoding task for episodic memory. This was a significant factor in dose selection because the intended AD-4833/TOMM40_301 study population is cognitively normal elderly adults, and the overall goal in dose selection was to minimize known dose-dependent adverse events (eg, edema) while ensuring that pioglitazone can still directly influence brain activity. Based on the available literature and the results of the fMRI study, pioglitazone sustained release (SR) 0.8 mg was selected for phase 3.

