For the summary of TEAEs by SOC, preferred term and maximum intensity, if a subject experiences more than one episode of a particular coded adverse event, the subject will be counted only once by the maximum intensity of the episode (preferred term). Similarly, if a subject has more than one adverse event within an SOC, the subject will be counted only once by the maximum intensity in that SOC. Adverse events with missing severity will be classified as having the highest severity.

TEAEs classified in the eCRF as related to the study medication will also be summarized by preferred term and SOC. If a subject experiences more than one episode of a particular coded adverse event, the subject will be counted only once by the most related report for the preferred term. Similarly, if a subject has more than one adverse event within an SOC, the subject will be counted only once by the most related report in that SOC. Adverse events with missing relationship will be classified as being related to study drug.

The following summaries will be presented:

- Overview of TEAEs during the study - number and percentage of subjects, number of events.
- TEAEs by SOC and preferred term - number and percentage of subjects, number of events.
- TEAEs by SOC and preferred term by gender (male and female) - number and percentage of subjects, number of events.
- TEAEs by SOC and preferred term by age group (<75, ≥75) - number and percentage of subjects, number of events.
- TEAEs by SOC - number and percentage of subjects.
- TEAEs by preferred term - number and percentage of subjects.
- Intensity of TEAEs by SOC and preferred term - number and percentage of subjects.
- Drug-related TEAEs by SOC and preferred term - number and percentage of subjects, number of events.
- TEAEs leading to study discontinuation by SOC and preferred term - number and percentage of subjects, number of events.
- Treatment-emergent SAEs by SOC and preferred term - number and percentage of subjects, number of events.

- Most frequent TEAEs and non-serious TEAEs ($\geq 5\%$ based on total number of safety set subjects in any treatment group) by SOC and preferred term - number and percentage of subjects, number of events.
- Adverse Events of Special Interest using the following categories defined in the protocol:
 - Congestive Heart Failure.
 - Macular Edema.
 - Hepatic Effects.
 - Bone Fractures.
 - Bladder Cancer.
 - Hypoglycemic Events.

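### Peripheral edema is the only warning listed in Protocol 4.1 without its own special-interest category, and no pooled edema term is pre-specified, so the plan gives no subject-level edema total by arm.

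*Protocol*

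**What the plan says.** Protocol 4.1 lists the adverse events from the Warnings and Precautions section of the core data sheet. They begin with "congestive heart failure (CHF) and peripheral edema due to dose-related fluid retention" and continue with "hepatic failure, increased incidence of fractures in female population, hypoglycemia, macular edema, and bladder cancer". The same sentence says that these arose in subjects with type 2 diabetes "at doses considerably higher (15-45 mg) than the intended dose".

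Protocol 4.1 also describes an 18-month pilot in nondiabetic subjects with AD, titrated to 45 mg/day, in which "peripheral edema was the principal AE (28.6% in pioglitazone-treated subjects compared with 0% in placebo-treated subjects". In Protocol 6.3.2, "the overall goal in dose selection was to minimize known dose-dependent adverse events (eg, edema") while still reaching the brain.

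Protocol 10.2.1.3 sets out six special-interest items: congestive heart failure (CHF), macular edema, hepatic effects, bone fractures, bladder cancer and hypoglycemia. Edema appears there only as an example of a sign of heart failure. SAP 9.14.1 plans a summary of "Adverse Events of Special Interest using the following categories defined in the protocol" and lists the same six.

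SAP 9.14.1 also tabulates treatment-emergent events by preferred term and by system organ class, with numbers and percentages of subjects. SAP 9.1.2 requires all three treatment groups in every tabulation. SAP 9.14.1 specifies no test or confidence interval for any adverse event or special-interest category.

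**The concern.** The protocol treats edema as a dose-related effect of the drug and uses it to explain the choice of dose. Long-term tolerability against placebo is a stated objective in cognitively normal people. One would therefore expect the analysis to state how many subjects in each arm had any edema event.

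The plan does not produce that number. A preferred-term row can be narrower than edema or fluid retention, and a system organ class row is broader. Related preferred-term rows cannot simply be added, because a subject with events under two terms would be counted twice. The CHF category does not supply the number either: Protocol 10.2.1.3 calls the signs of heart failure non-specific and stresses showing a cardiac cause, so edema without that diagnosis falls outside it.

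A modest excess spread over several rows is harder to see than the same excess in one row. A grouping chosen after unblinding would be open to the criticism that it was picked to suit the result.

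**Working it through.** **1. Warnings against categories.**

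| Warning (Protocol 4.1) | Special-interest category (Protocol 10.2.1.3, SAP 9.14.1) |
|---|---|
| CHF | Congestive heart failure |
| Peripheral edema | None; named only as a sign of CHF |
| Hepatic failure | Hepatic effects |
| Fractures in women | Bone fractures |
| Hypoglycemia | Hypoglycemia |
| Macular edema | Macular edema |
| Bladder cancer | Bladder cancer |

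Six of seven are covered; peripheral edema is the one left over.

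**2. The pilot figure.** The arms were 14 and 15 subjects. 4/14 = 28.6%, which reproduces the stated rate (3/14 = 21.4% and 5/14 = 35.7% do not). The exact 95% CI for 4/14 is 8.4% to 58.1%. Fisher's two-sided p for 4/14 versus 0/15 is 0.042. This is a small-sample signal at 45 mg/day and gives no rate for 0.8 mg SR.

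**3. Illustration of what pooling gains.** The arm size n = 1,470 is the estimated high-risk non-Hispanic/Latino Caucasian group (Protocol 6.1, SAP 6.4). The incidences and the share of cases in the largest preferred term are assumptions; the documents give neither.

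z = (pA − pP) / √[pA(1 − pA)/n + pP(1 − pP)/n]; chance that the 95% CI excludes zero ≈ Φ(z − 1.96).

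Worked case, 9% versus 6% pooled: 0.03 / √[(0.0819 + 0.0564)/1,470] = 0.03/0.00970 = 3.09, and Φ(1.13) = 0.87.

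| Assumed rates, pioglitazone vs placebo | Pooled event | Largest term holds 60% | Largest term holds 40% |
|---|---|---|---|
| 9% vs 6% | z 3.09, 87% | 5.4% vs 3.6%: z 2.36, 65% | 3.6% vs 2.4%: z 1.91, 48% |
| 6% vs 4% | z 2.49, 70% | 3.6% vs 2.4%: z 1.91, 48% | 2.4% vs 1.6%: z 1.55, 34% |

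**4. Frequent-event table.** SAP 9.14.1 lists events reaching 5% in any treatment group. In the first row of the table, a 9% pooled event would qualify. A largest term holding 40% of cases, at 0.4 × 9% = 3.6%, would not.

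**The case against.** The strongest reply is that edema is already displayed. A reader might infer from the missing category that edema is never compared between arms as one event. The documents do not support that: subjects with an event coded to a peripheral edema term are counted in one row, by treatment group, in the preferred-term table, and again in the intensity and drug-related tables where applicable. Fluid retention is also watched in other ways. Subjects are assessed for signs and symptoms of CHF, which include edema, at every visit (Protocol 10.2.1.3). Weight is summarized by group and visit with a flag for changes above 7% (SAP 9.14.3 and Appendix B), and the DSMB reviews all safety data (Protocol 11.2). All of this stands.

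The second reply is dose. The warnings come from 15-45 mg and the pilot from 45 mg/day, against 0.8 mg SR here. A reader might infer that edema is the most frequent harm to expect in this trial. The documents do not say so: the list in Protocol 4.1 of events above 5% and commoner on monotherapy than on placebo is headache, sinusitis, myalgia and pharyngitis. This stands too, but it does not explain the omission. The other six warnings come from the same dose range and have categories, including hypoglycemia, which Protocol 10.2.1.3 considers unlikely at low dose in elderly subjects without diabetes.

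Third, Protocol 4.1 links CHF and edema through a shared mechanism, so one may read them as a single entry that the CHF category covers. That is a defensible choice for expedited reporting. It does not give a count of subjects with edema but no heart failure.

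Finally, how far edema would split over terms cannot be read from the documents, someone reviewing the tables sees neighbouring rows together, and no existing category has a CI. The percentages above are therefore illustrative and do not measure a loss against a planned analysis.

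**Conclusion.** The point holds in a limited form. Peripheral edema is the only listed warning without its own category, and no pooled edema term is pre-specified. Edema without a heart failure diagnosis is therefore shown by arm only in routine tables that give no subject-level total across related terms. It does not follow that edema goes unmonitored or unreported, or that a high rate is expected at 0.8 mg SR.

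The size is uncertain. Under the assumed rates and term shares, the chance that a 95% CI excludes zero falls from 87% to 65% or 48%, or from 70% to 48% or 34%. If nearly all cases were coded to one term, almost nothing would be lost. The case for acting rests on the low cost and on fixing the grouping in advance. It is a minor improvement and does not affect the primary analyses.

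**What to change.** Add one pooled row, edema/fluid retention, to the special-interest summary in SAP 9.14.1. Fix its list of preferred terms before unblinding, and count subjects with at least one such event by treatment group. The grouped count is the essential part and matches what the existing categories receive. A high-risk pioglitazone minus high-risk placebo difference with a 95% CI may be added descriptively, although no existing category has one.

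Because SAP 9.14.1 says that its categories are those defined in the protocol, label the row as an analysis grouping so that it does not imply a new reporting duty. If the sponsor prefers not to add it, a sentence saying why none is needed would close the gap.

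The cost is a term list and one more safety row. No new data collection and no change in subject care are involved.

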4.2 Rationale for the Proposed Study

Zinfandel Pharmaceuticals, Inc. (Zinfandel) identified a genetic variant, translocase of the outer mitochondrial membrane 40 homolog (TOMM40) rs10524523, which appears to be prognostic of onset of cognitive decline within 5 years when combined with apolipoprotein E (APOE) genotype and age. The biomarker risk algorithm, which is the combination of TOMM40rs10524523 genotype, APOE and age, is used to categorize subjects as being either high-risk or low-risk to develop MCI due to AD within 5 years.

Zinfandel and Takeda entered into a license agreement pursuant to which Takeda is the exclusive licensee of the biomarker risk algorithm, including its use in evaluating the efficacy of pioglitazone for delaying the onset of MCI due to AD in high-risk individuals identified on the basis of the biomarker risk algorithm.

It has been estimated that delaying AD onset by 1 or 2 years could decrease global disease burden in 2050 by 11.8 million or 22.8 million cases, respectively [21]. Coupled with the failure of multiple treatment trials that have been conducted over the past decade, the focus of AD clinical research has begun to shift to the pursuit of a prevention strategy for AD, as brain

pathology may be too advanced to allow effective treatment of clinical symptoms, or disease modification, once patients are diagnosed with AD dementia.

However, few AD primary prevention studies have been conducted to date, and their results have been disappointing. In large (>2,000 subjects), long-term (planned as ≥ 5 years), randomized clinical trials of ginkgo biloba extract (GuidAge [22] and Ginkgo Evaluation of Memory Study [GEMS] [23]), hormone replacement therapy in women (Women's Health Initiative Memory Study [WHIMS] [24]), and non-steroidal anti-inflammatory drugs (NSAIDs) (Alzheimer's Disease Anti-inflammatory Prevention Trial [ADAPT] [25]) none of the primary, disease prevention objectives were achieved. Each of these studies employed an enrichment strategy to enroll subjects perceived to be at increased risk of developing AD or cognitive impairment. GEMS targeted the very old (≥ 75) and did not exclude individuals with MCI or milder cognitive syndromes; ADAPT targeted subjects with Alzheimer-like dementia in a first degree relative; WHIMS targeted postmenopausal women; and GuidAge enrolled individuals who spontaneously complained of memory problems to their general practitioner.

Like previous studies, this phase 3 study, AD-4833/TOMM40_301, will employ a strategy to enrich for at-risk subjects, in this case, those who are at-risk for developing MCI due to AD. The enrichment strategy is provided by the biomarker risk algorithm. The trial, therefore, is designed to pursue two primary objectives independently yet simultaneously: 1) to prospectively qualify the risk algorithm comprised of TOMM40 rs10524523 genotype, APOE genotype, and age as a biomarker for prognosis of an individual's risk of developing MCI due to AD in the next 5 years, and 2) to evaluate the efficacy of pioglitazone to delay the onset of MCI due to AD in cognitively normal subjects who are prognosed to be at high risk of developing MCI due to AD within 5 years. Subjects will be prospectively stratified into high-risk and low-risk groups on the basis of the risk algorithm and randomized to treatment with pioglitazone or placebo in the high-risk stratum or to placebo only in the low-risk stratum.

4.2.1 Genetic Risk Factors for AD

APOE epsilon genotype alone is neither sufficiently sensitive nor specific for clinical diagnosis of AD or prediction of age of onset of disease [26]. Roses et al have identified a second risk locus, in TOMM40, that provides greater resolution to the age of disease onset prediction, and for a greater proportion of the at-large population. Over a dozen genome wide association studies (GWAS) have confirmed the presence of a highly significant AD susceptibility locus within the TOMM40 gene, neighboring and in linkage disequilibrium (LD) with the well-known risk gene, APOE. Due to the LD between the genes, the association signal within TOMM40 has been previously attributed to APOE and thus overlooked.

In 2009, Roses et al. described the association between different lengths (short or S, long or L, and very long or VL) of a polyT locus (ie, the rs10524523 locus) in TOMM40 with ages of AD onset [27]. A phylogenetic analysis of high resolution sequence data from the region containing APOE and TOMM40 revealed the relationships between different alleles of TOMM40

rs10524523 and the APOE epsilon alleles, APOE ϵ 3 and APOE ϵ 4, in non-Hispanic/Latino Caucasian subjects. Long alleles of TOMM40 rs10524523 were nearly always linked to APOE ϵ 4 and associated with greater disease risk. In contrast, APOE ϵ 3 (and APOE ϵ 2) was linked to either short or very long TOMM40 rs10524523 alleles, with the short alleles associated with later disease onset and the very long alleles associated with earlier onset (mean onset ages of 77 years versus 70 years, respectively) in a cohort of autopsy-confirmed AD patients carrying the APOE ϵ 3/4 genotype. The association between APOE ϵ 4 and risk of development of AD, or age of AD onset, first reported by Roses et al in 1993, has been replicated in many case-control and cohort studies. However, only ~ 25% of Caucasians carry an APOE ϵ 4-containing genotype (2% are APOE ϵ 4/4, 20% are APOE ϵ 3/4, and 2% are APOE ϵ 2/4); therefore, this allele is potentially informative for a minority of the at-risk population. Further, APOE ϵ 4 carriage, alone, does not provide sufficient sensitivity, selectivity or predictive power to be used as a diagnostic or prognostic tool for AD [26,28]. While homozygosity for APOE ϵ 4 is informative for AD risk prediction in the clinic, it is rare and therefore not widely useful [29,30]. Stratification of age of onset by TOMM40 rs10524523 genotypes provides information for >97% of the at-risk population, as it addresses age-dependent risk for carriers of APOE ϵ 3, the most common allele, in addition to APOE ϵ 4 (see Figure 4.a [31]).

Figure 4.a Age of Onset of Cognitive Impairment as a Function of TOMM40 rs10524523 Genotype

[figure not shown]

Figure 4.a illustrates that the previously measured age of onset distribution for APOE $\epsilon 4/4$ subjects is identical to the TOMM40 rs10524523 L-L genotype distribution. The APOE $\epsilon 3/4$ curve can be deconvoluted into two curves corresponding to the two different alleles of TOMM40 rs10524523, S and VL, that can be connected to APOE $\epsilon 3$ (and to APOE $\epsilon 2$ alleles). Three TOMM40 rs10524523 age of onset curves, S/S, S/VL, and VL/VL account for the APOE $\epsilon 3/3$ and APOE $\epsilon 2/3$ genotypes. In the entire data set used to develop this figure, only 5 of 70 APOE $\epsilon 2$ allele carriers developed the clinical disease criteria and for the 5 individuals, this occurred after age 75 years on the three different curves (VL/VL, S/VL, and S/S). For the purpose of enrichment in this study, which will enroll subjects aged 65 to 83 years, inclusive, APOE $\epsilon 2/2$ and APOE $\epsilon 2/3$ carriers will be placed in the low risk stratum, while APOE $\epsilon 2/4$ subjects will be stratified to the high-risk stratum because these subjects also carry an APOE $\epsilon 4$ allele. Thus, TOMM40 rs10524523 and APOE genotypes may differentiate subjects at higher and lower age-dependent risk of developing MCI due to AD, and subsequently AD.

4.2.2 Pioglitazone

It has been suggested that PPAR- γ agonists could be effective in treating AD by regulating multiple pathogenic pathways in the central nervous system, including amyloid β homeostasis, insulin sensitivity, energy metabolism, lipid metabolism, and inflammation [32]. PPAR- γ agonists are insulin-sensitizing agents that allow the body to use endogenous insulin efficiently, maintaining the normal physiological feedback mechanisms, and producing minimal hypoglycemia. There is ample documentation that glucose utilization is impaired in brain regions involved in cognition, including memory, in patients with AD. Indeed, it has been demonstrated that subjects at risk of developing AD exhibit impaired cerebral glucose metabolism decades before the typical ages of onset of late onset AD [33,34].

PPAR- γ agonists also play critical roles in energy metabolism due to their direct effects on mitochondrial function and ultimately ATP production and neuronal glucose utilization. Mitochondria may be key players in the cerebral hypometabolism observed in AD, as this organelle plays critical roles in energy metabolism, neuronal apoptosis and the maintenance of synapses. In AD-affected brain, the mitochondria have altered morphology, including an increased proportion of damaged mitochondria, altered distribution within neurons, and there is a decrease in the amounts of enzyme complexes that are essential for ATP production [35]. The effects of PPAR- γ agonists on mitochondria structure and function may be the basis of their beneficial effects on cognition, including memory, in AD subjects [12,36].

A paramount consideration for development of a preventive measure is its safety, set at a particularly high threshold given that the intended study population is cognitively normal. While some side effects may be acceptable to individuals already affected by the devastating symptoms of AD, only few, reversible, and minor adverse drug reactions would be acceptable to cognitively-normal individuals who may or may not decline to AD dementia. Ideally, an active pharmaceutical agent for a delay of MCI due to AD indication would be supported by extensive exposure data gathered through multiple years and in thousands of patients globally. While extensive drug exposure data exist for the two marketed TZDs, pioglitazone is widely considered to be safer than rosiglitazone. The favorable safety profile of pioglitazone was underscored by the meta-analysis presented at the Food and Drug Administration (FDA) Joint Meeting of the Endocrinologic and Metabolic Drug Advisory Committee and the Drug Safety and Risk Management Advisory Committee Meeting, 2010 [37]. The meta-analysis included 35 trials covering 22,131 patients, of whom 12,213 (55%) were randomized to pioglitazone and 9,918 (45%) to the comparator. Overall, across all trials for pioglitazone, the estimated MACE (major adverse cardiovascular events, defined as cardiovascular death, stroke or myocardial infarction) risk was lower for pioglitazone compared to control (hazard ratio [HR]=0.80; 95% confidence interval [CI]=0.70-0.93).

